6.3.2 Hypoglycemia Events

During the study, participants must be instructed to document any hypoglycemia events in their eDiary. Hypoglycemia will be reported in the specific hypoglycemia event information form in the eCRF with onset date and time; symptoms and/or signs; the SMPG value, if available; and the treatment. A hypoglycemia event that fulfills the seriousness criteria will also be documented on the SAE form in the eCRF.

Hypoglycemia will be evaluated in accordance with the consensus report of a steering committee on levels of hypoglycemia (Agiostratidou et al 2017). These levels are consistent with ADA standard of care 2021 recommendations (ADA 2021a).

The following are the categories of interest:

- Overall hypoglycemia.
- Confirmed hypoglycemia.
 - ADA Level 1: A measurable glucose concentration of <70 mg/dL (3.9 mmol/L) but ≥54 mg/dL (3.0 mmol/L) that can alert a person to take action. Blood glucose concentration of 70 mg/dL (3.9 mmol/L) has been recognized as a marker of physiological hypoglycemia in humans. Recurrent episodes of hypoglycemia lead to increased hypoglycemia unawareness, Therefore, glucose levels <70 mg/dL (3.9 mmol/L) are clinically important, independent of the severity of acute symptoms.
 - ADA Level 2: A measurable glucose concentration of <54 mg/dL (3.0 mmol/L) that needs immediate action. At approximately 54 mg/dL (3.0 mmol/L), neurogenic and neuroglycopenic hypoglycemia symptoms begin to occur, ultimately leading to brain dysfunction at levels <50 mg/dL (2.8 mmol/L). Neuroglycopenic symptoms, including behavioral changes, visual changes, seizure, and loss of consciousness, are the result of central nervous system neuronal glucose deprivation.
 - ADA Level 3: A severe event characterized by altered mental and/or physical functioning that requires assistance* from another person for recovery. Severe hypoglycemia captures events during which the symptoms associated with hypoglycemia affect a patient such that the patient requires assistance from others.

*Note that "requires assistance" means that the person could not help themselves. Assisting a person out of kindness, when assistance is not required, should not be considered a "requires assistance" incident.

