4.7.3 Hypoglycemia events

During the study, participants are to be instructed to document any hypoglycemic episodes in their e-diary. Hypoglycemia will be reported on the specific eCRF page with onset date and time, symptoms and/or signs, the glucose measurement obtained at the time of the event before countermeasures, the collection date and time of glucose measurement, and the treatment of hypoglycemia. Hypoglycemia meeting the definition of an adverse event will be documented, in addition, on the AE form in the eCRF.

The following hypoglycemia events are the categories of interest:

- Any Hypoglycemia Event: Any event recorded in Hypoglycemic Event Information Library eCRF page that has “Yes” as the response to the question “Were any hypoglycemic events experienced”, regardless of the plasma glucose measurements.
- ADA Level 1 Hypoglycemia: A measurable glucose concentration of <70 mg/dL (3.9 mmol/L) but ≥54 mg/dL (3.0 mmol/L) that can alert a person to take action. A blood glucose concentration of 70 mg/dL (3.9 mmol/L) has been recognized as a marker of physiologic hypoglycemia in humans. Recurrent episodes of hypoglycemia lead to increased hypoglycemia unawareness. Therefore, glucose levels <70 mg/dL (3.9 mmol/L) are clinically important, independent of the severity of acute symptoms. The event will be captured if the Glucose Measurement in the Hypoglycemic Event Information Library eCRF page falls within the described blood glucose concentration levels.

- ADA Level 2 Hypoglycemia: A measurable glucose concentration of <54 mg/dL (3.0 mmol/L) that needs immediate action. At approximately 54 mg/dL (3.0 mmol/L), neurogenic and neuroglycopenic hypoglycemia symptoms begin to occur, ultimately leading to brain dysfunction at levels <50 mg/dL (2.8 mmol/L). Neuroglycopenic symptoms, including behavioral changes, visual changes, seizure, and loss of consciousness, are the result of central nervous system neuronal glucose deprivation. The event will be captured if the Glucose Measurement in the Hypoglycemic Event Information Library eCRF page falls within the described blood glucose concentration levels.

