- ADA Level 3 Hypoglycemia: A severe event characterized by altered mental and/or physical functioning that requires assistance from another person for recovery due to participant's inability to help themselves. Severe hypoglycemia captures events during which the symptoms associated with hypoglycemia affect a participant such that the participant requires assistance from others. The event will be captured if the Glucose Measurement in the Hypoglycemic Event Information Library eCRF page falls within the described blood glucose concentration levels and if "Required Assistance because subject was not capable of helping self" was selected.
- Documented Hypoglycemia: (<70 mg/dL): a glucose level of <70 mg/dL (or <3.9 mmol/L) (with or without symptoms).
 - Documented Symptomatic Hypoglycemia (<70 mg/ dL): defined as an event during which typical symptoms of hypoglycemia are accompanied by a measured plasma glucose concentration less than 70 mg/dL (3.9 mmol/L). Clinical symptoms that often result from a hypoglycemic episode can include (but not necessarily limited to) increased sweating, nervousness, asthenia/weakness, tremor, dizziness, increased appetite, palpitations, headache, sleep disorder, confusion, seizures, unconsciousness, or coma.
 - Documented Symptomatic Hypoglycemia will be identified in the Hypoglycemic Event Information Library eCRF page in those who indicated "symptoms were present" with a measured plasma glucose value <70 mg/dL (or <3.9 mmol/L)
 - Documented Serious Symptomatic Hypoglycemia: defined as an event where the participant also requires assistance from another person for recovery due to participant's inability to help themselves, i.e., identified in the Hypoglycemic Event Information Library eCRF page, as "Required assistance because subject was not capable of helping self".
 - Documented Non-serious Symptomatic Hypoglycemia: defined as an event where the participant does not require assistance from another person for recovery, i.e., identified in the Hypoglycemic Event Information Library eCRF page, with a "No Assistance" response or "Received Assistance but Subject Was Capable of Helping Self".
 - Documented Asymptomatic Hypoglycemia: asymptomatic hypoglycemia is defined as an event not accompanied by typical symptoms of hypoglycemia but with a measured plasma glucose concentration < 70 mg/dL (or <3.9 mmol/L) i.e., identified in the

Hypoglycemic Event Information Library eCRF page with a “No” response to “Were symptoms present”.

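### SAP 4.7.3 makes ADA Level 3 hypoglycemia depend on a glucose range it never gives, so an assisted event with no glucose value counts at no ADA level

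*SAP*

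**What the plan says.** SAP 4.7.3 gives each ADA level a definition followed by a capture rule based on the hypoglycemia eCRF page.

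- **Level 1:** "A measurable glucose concentration of <70 mg/dL (3.9 mmol/L) but ≥54 mg/dL (3.0 mmol/L) that can alert a person to take action". Captured if the recorded glucose lies in that range.
- **Level 2:** "A measurable glucose concentration of <54 mg/dL (3.0 mmol/L) that needs immediate action". Captured the same way.
- **Level 3:** defined by altered functioning and inability to help oneself, with the explanation "Severe hypoglycemia captures events during which the symptoms associated with hypoglycemia affect a participant such that the participant requires assistance from others". It is captured if the recorded glucose "falls within the described blood glucose concentration levels and if" the option for required assistance was selected.

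The eCRF glucose is "the glucose measurement obtained at the time of the event before countermeasures".

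Protocol 6.3.2 defines Level 3 as "A severe event characterized by altered mental and/or physical functioning that requires assistance* from another person for recovery", with no glucose threshold. The protocol synopsis, Protocol Table 2-3 and SAP Table 2 say the same. Protocol 6.3.2 also has the SMPG value reported only where one exists, and Protocol 6.2.3.1 lets rescue come before measurement when safety demands it.

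SAP Appendix 2 declares no change to the protocol-planned analyses, and Table 9 in SAP Appendix 5 does not list this one.

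**The concern.** The capture sentence works for Levels 1 and 2 because their bullets state ranges. Under Level 3 it points to a range that is not there. Joining the two conditions with *and* also adds a glucose requirement that the protocol's definition of the endpoint does not have.

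The people most exposed to this are those in a Level 3 event. Someone who cannot help themselves may well be treated before anyone takes a reading.

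Level 3 is a named safety endpoint. Its row appears in five by-level summaries in SAP 4.7.3: one by ADA level, and four by time of day (nocturnal by clock and by sleep status, daytime by clock and by awake status). The hypoglycemia summaries are repeated for four subgroups. An undercount would run through all of these, in a single-arm study of insulin-naïve participants where one event can decide whether the row reads zero.

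**Working it through.** The plan states no figure to reproduce, so the check is to apply the written rules to possible events.

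**Inputs.** Level 1 is 54 to below 70 mg/dL and Level 2 is below 54 mg/dL (SAP 4.7.3). Level 3 was applied four ways: by assistance alone (the protocol); by the SAP rule with no range, which no event can satisfy; by the SAP rule borrowing <70; and by the SAP rule borrowing <54. Every event below required assistance.

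| Recorded glucose | Protocol | SAP, no range | SAP, <70 | SAP, <54 |
|---|---|---|---|---|
| none | 3 | no level | no level | no level |
| 75 mg/dL | 3 | no level | no level | no level |
| 60 mg/dL | 1 and 3 | 1 | 1 and 3 | 1 |
| 48 mg/dL | 2 and 3 | 2 | 2 and 3 | 2 and 3 |

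With no value, the event is at no ADA level on any SAP reading. At 70 mg/dL or above the result is the same. At 54 to 69 mg/dL the answer depends on the borrowed range.

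**Do other SAP 4.7.3 categories pick up the event with no value?**

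- Documented hypoglycemia needs a value below 70 mg/dL. The assisted sub-category, "Documented Serious Symptomatic Hypoglycemia: defined as an event where the participant also requires assistance from another person for recovery", sits under it and inherits that condition.
- Symptomatic hypoglycemia needs a value below 70 mg/dL, and pseudohypoglycemia needs one of 70 mg/dL or above.
- Any Hypoglycemia Event keeps it, "regardless of the plasma glucose measurements", but without its severity. The overall time-of-day rows keep it too.
- AE or SAE forms record it if it qualifies. The listing of severe events probably shows it, since severe is described by need for assistance.

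None of these restores the Level 3 count. If <70 is borrowed, the Level 3 row also largely repeats the Documented Serious Symptomatic row, leaving no by-level count based on assistance alone.

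**Illustrative size.** Assume 95 to 100 of the 100 planned participants are treated, that exactly one Level 3 event occurs, and that it has no value. The exact (Clopper-Pearson) 95% limits for x of n are the 0.025 quantile of Beta(x, n−x+1) and the 0.975 quantile of Beta(x+1, n−x). For x = 0 the lower limit is 0 and the upper is 1 − 0.025^(1/n).

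- 0/100: upper limit 1 − 0.025^(1/100) = 3.62%.
- 1/100 = 1.0%: 0.025% to 5.45%.
- 0/95: upper limit 1 − 0.025^(1/95) = 3.81%.
- 1/95 = 1.05%: 0.027% to 5.73%.

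**The case against.** The best defence is that the glucose condition is deliberate. The protocol and SAP Table 2 list Levels 1 to 3 under confirmed hypoglycemia, and requiring a value is a plausible way to make that word operational. On this view the described levels are those of Levels 1 and 2 together, that is, anything below 70 mg/dL, and the only fault is an unstated threshold. The heading, however, supplies no range, and the Level 3 text beneath it sets none. Reading <70 into the rule removes the ambiguity at 54 to 69 mg/dL but still drops the event with no value. A deliberate narrowing of a named endpoint should have been declared, and it was not.

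Second, the planned figure shows time to first severe or documented Level 3 symptomatic event, so an unmeasured assisted event may enter there as well as in the listing. That is plausible, although severe has no capture rule of its own. It would leave the figure disagreeing with the by-level tables.

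Third, dropping the glucose condition lets an assisted symptomatic event at 70 mg/dL or above be both Level 3 and pseudohypoglycemia. That is true, but these reporting rows are not mutually exclusive, and the added counts under the fix show the overlap.

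Two limits stand. Safety is descriptive with no testing (SAP 4.7), and the size is hypothetical. The SAP rule also says *if* and not *only if*, but it is the only Level 3 capture rule given.

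**Conclusion.** The concern holds. As written, the Level 3 rule refers to a range that does not exist and departs, undeclared, from the protocol's assistance-based definition. An assisted event without a glucose value counts at no ADA level however the rule is read, and one at 54 to 69 mg/dL is classified according to a choice the SAP does not make.

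The number of events affected is unknown. The 1-versus-0 illustration rests on its stated assumptions and is not a forecast. The event is not lost from the study data, and the efficacy conclusions do not depend on it. The rule should be corrected because it can undercount the most serious hypoglycemia category.

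**What to change.** In SAP 4.7.3, replace the Level 3 capture sentence with one to this effect: *The event is captured if the eCRF option recording that assistance was required because the participant could not help themselves was selected; a glucose value is not required.*

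Report beside it the number of Level 3 events with no glucose value and the number with a value of 70 mg/dL or more. Use the same definition in the by-level tables, the severe-event listing and the time-to-first-event figure. The Documented, Symptomatic and Pseudohypoglycemia definitions can stay.

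The cost is one sentence, one programming condition and two counts, with no new data, since the assistance field is already on the eCRF. The downside is that the Level 3 count may be slightly higher and include some events without glucose confirmation; the two counts make those visible.

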6.2.3.1 SMPG During Symptomatic Hypoglycemia

Whenever participants experience hypoglycemia symptoms, they (or others, if applicable) should measure plasma glucose, if possible. Participants should be instructed to measure plasma glucose levels before carbohydrate intake/administration of glucose whenever symptomatic hypoglycemia is suspected, unless safety considerations necessitate immediate carbohydrate/glucose rescue before confirmation with the SMPG values. Participants must contact the investigator as soon as possible following hypoglycemia events for review and so

Property of the Sanofi Group - strictly confidential

that a decision regarding any necessary actions can be made. Participants should be instructed to measure plasma glucose levels again after the event resolves.

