
- Symptomatic Hypoglycemia: defined as any symptomatic hypoglycemia recorded on Hypoglycemic Event Information Library eCRF page responding that symptoms were present with the plasma glucose measurements of < 70 mg/dL (or < 3.9 mmol/L).
- Pseudohypoglycemia: defined as any symptomatic hypoglycemia recorded on Hypoglycemic Event Information Library eCRF page responding that symptoms were present with the plasma glucose measurements of ≥ 70 mg/dL (or ≥ 3.9 mmol/L).

Hypoglycemia events categorized by time of day at which the event occurred by ADA levels, will be provided in a table:

- Nocturnal Hypoglycemia Defined by Time of the Day: Any hypoglycemia event that occurs between 00:00 and 05:59, regardless of whether the participant was awake or woke up because of the event.
- Nocturnal Hypoglycemia Defined by Sleep Status: Any hypoglycemia event that wakes the participant from sleep between bedtime and rising in the morning, i.e., before the morning assessment of fasting prebreakfast SMPG and before any insulin injection. The participant wakes up because of the event.
- Daytime Hypoglycemia Defined by Time of the Day: Any hypoglycemia event that occurs between 06:00 and 23:59.
- Daytime Hypoglycemia Defined by Awake Status: Any hypoglycemia event that occurs between the participant waking up and going to sleep.

Hypoglycemia observation periods

- Pre-treatment hypoglycemia events are events that developed or worsened or became serious from the signed informed consent date up to first administration of the IMP.
- Treatment-emergent hypoglycemia events are those that developed or worsened or became serious during the on-treatment period arising from the time of the first IMP administration (on Day 1) up to 1 day after the last IMP injection.
- Post-treatment hypoglycemia events are events that developed or worsened or became serious during the post-treatment period arising 1 day after the end of the TEAE period up to the end of the study follow-up (2 weeks after the end of treatment period)

Descriptive analysis will summarize hypoglycemia events in a table (repeat for subgroups [i.e., OAD only at baseline, OAD plus GLP-1 RA at baseline, ≥ 65 years of age, < 65 years of age]):

- Overall number and percentage of participants with at least 1 hypoglycemia event (for overall and each observation period) and number of hypoglycemic events (for overall and each observation period)

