- Number and percentage of participants with at least 1 hypoglycemia event and number of hypoglycemic events, by ADA classification levels

- Number and percentage of participants with at least 1 hypoglycemia event and number of hypoglycemic events, by observation periods
- Documented Hypoglycemia
 - Documented symptomatic hypoglycemia
 - Documented serious symptomatic hypoglycemia
 - Documented non-serious symptomatic hypoglycemia
 - Asymptomatic Hypoglycemia
- Symptomatic Hypoglycemia
- Pseudohypoglycemia
- Nocturnal Hypoglycemia Defined by Time of the Day, overall and by ADA levels
- Nocturnal Hypoglycemia Defined by Sleep Status, overall and by ADA levels
- Daytime Hypoglycemia Defined by Time of the Day: overall and by ADA levels
- Daytime Hypoglycemia Defined by Awake Status, overall and by ADA levels

In addition, rate of on-treatment symptomatic hypoglycemic events (Overall, and by time of day per ADA levels) will be summarized in a table whereas

Hypoglycemic events rate per participant year = Number with hypoglycemic events/Total Person Years

If there are multiple events from an individual participant, all events will be counted.

where Total PY is calculated as below:

Observation period	Total Person Years	Time to event (days)	Censoring time (days)
On-treatment	(cumulative total time to event date for participants with event + cumulative total of censoring time for participants without event)	date of event -first dose date +1	(last dose date+1) -first dose date +1

Participants with symptomatic hypoglycemia events, and participants with severe hypoglycemia events will be displayed in listings. A figure will be provided showing the time to the first severe or documented ADA Level 3 symptomatic hypoglycemia during on-treatment period.

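### SAP 4.7.3 defines Symptomatic Hypoglycemia by the same conditions as Documented Symptomatic Hypoglycemia, so symptomatic events with no glucose value fall in no symptomatic row

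*SAP*

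**What the plan says.** SAP 4.7.3 defines Documented Symptomatic Hypoglycemia as an event in which "typical symptoms of hypoglycemia are accompanied by a measured plasma glucose concentration less than 70 mg/dL (3.9 mmol/L"). The data rule that follows begins "Documented Symptomatic Hypoglycemia will be identified in the Hypoglycemic Event Information Library eCRF page in those who indicated" symptoms, and ends "with a measured plasma glucose value <70 mg/dL (or <3.9 mmol/L").

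Later in the same section stands "Symptomatic Hypoglycemia: defined as any symptomatic hypoglycemia recorded on Hypoglycemic Event Information Library eCRF page responding that symptoms were present with the plasma glucose measurements", the cut-off again being under 70 mg/dL. Pseudohypoglycemia is a symptomatic event with a value of 70 mg/dL or more. Any Hypoglycemia Event is the only category defined without regard to glucose. The value the eCRF page is to hold is the one taken before countermeasures.

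The table plan at the end of SAP 4.7.3 lists Documented Symptomatic and Symptomatic Hypoglycemia as separate rows. It then adds that the "rate of on-treatment symptomatic hypoglycemic events (Overall, and by time of day per ADA levels) will be summarized in a table", together with a listing of participants with symptomatic events.

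The protocol expects some events to have no value. Section 6.2.3.1 asks participants to measure before taking carbohydrate, "unless safety considerations necessitate immediate carbohydrate/glucose rescue before confirmation with the SMPG values". Section 6.3.2 has the event form record "the SMPG value, if available".

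Two other places plan a wider rate. SAP 4.7 promises hypoglycemia events per participant-year without restricting them to symptomatic events, and refers forward to the hypoglycemia section. Protocol 8.7.8.2 plans a rate per person-years for hypoglycemia events, overall and by level.

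**The concern.** Two rows with different names should answer different questions. Usually the broader symptomatic category holds every event with symptoms that is not contradicted by a glucose reading, and the documented category holds the confirmed subset. Here both require the confirming value, so one row adds nothing and the gap the broader row would fill stays open.

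The events that fall into the gap are those in which the participant treated first and no pre-treatment value was recorded. The protocol links treating first to safety need, so some of them may be the more urgent ones, although no figure in the documents shows this. The study drug contains insulin and the protocol names hypoglycemia among its important identified risks. A reader of the symptomatic rate would want to know whether untested events are in it.

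**Working it through.** There is no planned figure to reproduce; the check is on the definitions.

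**Step 1: apply the rules.** Each SAP 4.7.3 category was written as a rule on symptoms (yes, no), glucose (missing, 50, 65, 69, 70, 90 mg/dL) and assistance (yes, no), giving 2 × 6 × 2 = 24 combinations. For the symptomatic ones:

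| Recorded event | Documented Symptomatic | Symptomatic | Pseudohypoglycemia | Any Hypoglycemia Event |
|---|---|---|---|---|
| Symptoms, glucose 50, 65 or 69 | yes | yes | no | yes |
| Symptoms, glucose 70 or 90 | no | no | yes | yes |
| Symptoms, no glucose value | no | no | no | yes |

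Membership of the first two categories agrees in all 24 combinations, so the rows must be equal whatever the data. Of the categories coded, a symptomatic event with no value belongs only to Any Hypoglycemia Event, with or without assistance. It is also outside ADA Levels 1 to 3 as the SAP codes them. For Level 3 the SAP asks for a glucose value within levels it does not give, while protocol 6.3.2 sets no glucose condition for that level.

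**Step 2: follow the definition to the rate.** The rate in SAP 4.7.3 is for on-treatment symptomatic events. The section does not cite a definition there, and its formula speaks only of hypoglycemic events. Symptomatic Hypoglycemia is, however, a defined category of the same section, so reading the rate and the listing by that definition is the natural inference.

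**Step 3: size.** Let S be symptomatic events with glucose under 70 mg/dL, U those with no value, and m = U/(S + U). Let T be person-time with all S + U events counted and T′ person-time with only the S events counted. Then

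rate as defined / rate with no-value events = (1 − m) × T/T′.

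The documents give no m. If T′ = T, assumed values of m = 5%, 10%, 20% and 30% give ratios of 0.95, 0.90, 0.80 and 0.70.

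T′ need not equal T, because SAP 4.7.3 stops person-time at the event date for participants with an event. An illustration with assumed figures: 100 participants, 20 with one event each at day 57, 3 of these with no value (m = 3/20 = 15%), the others censored at day 114 (first dose Day 0, last dose Day 112, SAP formula 112 + 1 + 1).

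- All 20 events: T = 80 × 114 + 20 × 57 = 10,260 days; 20/10,260 × 365.25 = 0.712 per year.
- Only the 17 with a value: T′ = 83 × 114 + 17 × 57 = 10,431 days; 17/10,431 × 365.25 = 0.595 per year.
- Ratio 0.595/0.712 = 0.836, a fall of 16.4% against m = 15%.

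The shortfall is therefore close to the untested share but not equal to it.

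**The case against.** The strongest reply is that little is lost. Events with no value stay in Any Hypoglycemia Event, in the overall counts of participants and events by observation period, and in the overall nocturnal and daytime rows, which are defined on any event. Those that qualify as adverse events also reach the AE tables. The declared safety endpoints are overall and confirmed hypoglycemia by ADA level; symptomatic hypoglycemia is not among them, and the safety analysis is descriptive. All of this stands and limits the weight of the point.

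A reader might infer that the plan gives event rates for symptomatic hypoglycemia only, so that a principal safety rate is understated. The documents do not support that. SAP 4.7 and protocol 8.7.8.2 both plan a rate not limited to symptomatic events, and SAP 5.2 declares no changes to protocol-planned analyses. What can be said is that SAP 4.7.3, where the detail belongs, does not carry that rate through.

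It can also be argued that requiring a value is a legitimate choice. Some untested events may not be true hypoglycemia, as the pseudohypoglycemia category itself recognizes, and an event with no value cannot be placed in the glucose-based ADA levels. This is a fair reason not to pool untested events silently into a single rate. It does not justify two identical rows and none for the untested events.

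Finally, the group may be smaller than it looks, because protocol 6.2.3.1 asks for a measurement after the event resolves. A site that entered that later value could move the event into Symptomatic Hypoglycemia or Pseudohypoglycemia. The SAP gives no rule for this, so it leaves the classification less certain.

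**Conclusion.** The point holds. That the two rows coincide, and that symptomatic events with no value are in neither of them nor in Pseudohypoglycemia, follows directly from the SAP's wording. That these events are also missing from the symptomatic rate and listing is an inference, though the natural one.

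The size cannot be derived from the documents. Under an assumed untested share of 5% to 30%, the symptomatic rate would be roughly 5% to 30% lower than with those events included. It would be wrong to call the shortfall exactly the untested share, since the person-time rule changes the denominator too. The range also takes the no-value events as belonging in the category, which cannot be verified for each one.

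This is an avoidable gap in a descriptive safety table. It does not touch the primary endpoint or remove events from the overall hypoglycemia counts. It should be corrected because the rate it affects is the only one that SAP 4.7.3 spells out.

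**What to change.** In SAP 4.7.3:

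- Define Symptomatic Hypoglycemia as symptoms present with glucose under 70 mg/dL or with no recorded glucose value.
- Show two subsets as separate rows: documented (under 70 mg/dL) and no glucose value. Leave Pseudohypoglycemia as it is.
- State which definition feeds the event rate. Report the overall symptomatic rate for the full category and for the documented subset, and keep the ADA-level splits for events with a value.
- Add the all-event hypoglycemia rate that SAP 4.7 and protocol 8.7.8.2 plan.

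The cost is one changed definition, one added row and two added rates. Symptoms and glucose are already recorded separately on the eCRF page, so no new data are needed and nothing changes for participants. The downside is that some untested events may not be true hypoglycemia; the separate rows and the paired rates let the reader see how much depends on them.
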